6.3. Analyses of Exploratory Efficacy Endpoints

6.4. Subgroup Analysis

To determine whether the treatment effect is consistent across various subgroups, the primary endpoint will be provided, where feasible, within each category of the following classification variables (subcategories under a specific category of a variable, where applicable, are indicated in brackets):

Demographic subgroups

- Sex (male, female)
- Age (< 65, \geq 65 years)
- Baseline weight (< 70, \geq 70 to < 85, \geq 85 to < 100, \geq 100 kg)
- Baseline BMI (< 25, \geq 25 to < 30, \geq 30 to < 35, \geq 35 to < 40, \geq 40 kg/m²)
- Region (North America, Europe, Rest of the World [including Russia])
- Prior glucocorticosteroid use (yes, no)
- Prior use of MTX (Yes/No)
- Concomitant use of MTX (Yes/No)

Baseline disease subgroups

- Duration of PsA (\geq 3 months to \leq 2, > 2 to \leq 5 years)

The consistency of the treatment effect across subgroups will be assessed in the context of the primary methods used for the analyses with the entire FAS.

7. INTERIM ANALYSIS

No interim analysis will be conducted.

At the end of the study, after all subjects have completed the treatment period or early terminated, the final analysis will be performed, and a final clinical study report will be generated.

8. Summary of Subject Disposition

The number of subjects screened, the number and percentage of subjects, who complete screening, who do not complete screening, and who are screen failure among all subjects screened, and the eligibility criteria failed will be summarized. The above percentages will be based on the number of subjects screened.

For this single-arm, open-label study, the number and percentage of subjects who enroll, receive at least one dose of IP, complete, and discontinue, and the number and percentage of primary reasons for discontinuation (except for the observational follow-up) will be summarized. The number and percentage of subjects who enter/complete the observational follow-up, will also be provided. The primary reasons for discontinuation are collected in the study disposition eCRF and will be summarized with the following categories:

- Adverse event(s)
- Lack of efficacy
- Non-compliance with study drug
- Withdrawal by subject
- Study terminated by sponsor
- Lost to follow-up
- Pregnancy
- Death
- Protocol deviation
- Other

The number and percentage of subjects included in the FAS, mITT, PP, and safety populations will be summarized; the percentages will be based on the number of subjects enrolled. A listing of subjects excluded from the analysis populations, with the reasons for exclusions, will be provided.

The number and percentage of subjects by region, country, and study site will be tabulated based on the FAS.

9. Demographics and Baseline Characteristics

Demographics and baseline characteristics will be summarized descriptively for the FAS. Each relevant characteristic will be assessed descriptively in table format; no statistical hypothesis tests will be performed on these characteristics.

For summaries (number and percentage) of categorical variables in demographics, baseline disease characteristics, and alcohol and tobacco use, an “unknown” category may be added (in addition to the categories specified below) to account for missing data as appropriate.

9.1. Demographics

Summary statistics will be provided for the following continuous variables as appropriate:

- Age (years)
- Weight (kg)
- Height (cm)
- Body mass index (BMI; kg/m²)

Number and percentage will be provided for the following categorical variables as appropriate:

[figure not shown]
- Age category (< 65, ≥ 65 years; < 40, 40 to < 65, 65 to < 75, 75 to < 85, ≥ 85 years)
- Sex (male, female)
- Race (American Indian or Alaska Native, Asian, Black or African American, Native Hawaiian or Other Pacific Islanders, White, Other)
- Ethnicity (Hispanic or Latino, not Hispanic or Latino)
- Region (North America, Europe, Rest of the World [including Russia])
- Weight category (< 70, ≥ 70 to < 85, ≥ 85 to < 100, ≥ 100 kg)
- BMI category (< 25, 25 to < 30, 30 to < 35, 35 to < 40, ≥ 40 kg/m²)

9.2. Baseline or Disease Characteristics

Summary statistics will be provided for the following continuous variables as appropriate:

- Duration of PsA (from the date of diagnosis to the date of informed consent; years)
- Psoriasis body surface area (BSA; %)
- Inflammation score of BME, synovitis, and tenosynovitis assessed by PsAMRIS
- Composite score of BME and synovitis assessed by PsAMRIS
- BME score assessed by PsAMRIS
- Synovitis score assessed by PsAMRIS

- Tenosynovitis score assessed by PsAMRIS
- Periarticular inflammation score assessed by PsAMRIS
- Total damage score (bone erosion + bone proliferation) assessed by PsAMRIS
- Bone erosion score assessed by PsAMRIS
- Bone proliferation score assessed by PsAMRIS
- Tender joint count
- Swollen joint count
- C-DAPSA score
- SPARCC score
- SPARCC score (for subjects with pre-existing enthesopathy)
- LEI score
- LEI score (for subjects with pre-existing enthesopathy)
- LDI score
- LDI score (for subjects with pre-existing dactylitis)
- PASDAS score
- Physician global assessment of disease activity (0-10 NRS)
- Subject global assessment of disease activity (0-10 NRS)
- Subject assessment of pain (0-10 NRS)
- HAQ-DI score
- Peripheral enthesitis inflammation index assessed by WB-MRI
- Peripheral joints inflammation index assessed by WB-MRI
- Total peripheral (joints and enthesitis) inflammation index assessed by WB-MRI
- BASDAI score (for subjects deemed to have PsA spondylitis by the investigator and with BASDAI item 2 \geq 4 at baseline)
- PsAID-12 score

Number and percentage will be provided for the following categorical variables (subcategories under a specific category of a variable, where applicable, are indicated in square brackets) as appropriate:

- Baseline use of methotrexate (MTX) (yes, no)
- Psoriasis BSA $\geq 3\%$ (yes, no)
- Prior use of NSAIDs
- Prior use of low-dose oral glucocorticoids (prednisone ≤ 10 mg/day or equivalent)
- Prior use of narcotic analgesics (yes, no)
- Rheumatoid factor (normal, high)
- Pre-existing SPARCC enthesopathy (yes, no)
- Pre-existing LEI enthesopathy (yes, no)
- Pre-existing dactylitis (yes, no)
- PsA spondylitis assessed by investigator (yes, no)

- BASDAI item 2 ≥ 4 (yes, no)
- PsA spondylitis assessed by investigator and BASDAI item 2 ≥ 4 (yes, no)
- Prior csDMARD usage (yes, no)
- Prior biologic treatment (yes, no)
- C-DAPSA (≤ 4 , >4 to ≤ 13 , >13 to ≤ 27 , >27)
- As based on the trial design (Section 4.1) and permitted concomitant medications and procedures from protocol, MTX (≤ 25 mg/week) will be permitted if treatment duration is ≥ 6 months and on a stable regimen for at least 3 months prior to baseline. The NSAIDs, narcotic analgesics and low-dose oral glucocorticoids (prednisone ≤ 10 mg/day or equivalent) must be on a stable regimen for at least 4 weeks prior to baseline. Thus, baseline use of MTX is defined as MTX (≤ 25 mg/week) used as a stable regimen for at least 3 months before the first dose of IP. For the NSAIDs, narcotic analgesics and low-dose oral glucocorticoids medications, the baseline use of these medications are defined as medications used as a stable regimen for at least 4 weeks before the first dose of IP.

9.3. Medical History

Medical history will be coded according to the Medical Dictionary for Regulatory Activities (MedDRA; Version 21.0). A frequency summary (number and percentage) of medical history will be presented by system organ class (SOC), and preferred term (PT).

9.4. Prior Medications

Prior medications will be collected from prior and concomitant medications and history of psoriatic arthritis medications panels in the CRF pages. The prior medications are defined as medications that were taken before the first dose of IP. The Anatomical Therapeutic Chemical (ATC) coding scheme of the World Health Organization Drug Dictionary (WHODD; Version March 2018) will be used to group prior medications and history of psoriatic arthritis medications into relevant categories. Frequency summaries will be provided by ATC 2 level, and standardized medication name for the FAS population.

9.5. Prior Procedures

Prior procedures are defined as the procedures that occurred before the first dose of IP. The prior procedures will be coded using the Medical Dictionary for Regulatory Activities (MedDRA; Version 21.0). Frequency summaries of prior procedures will be provided for the FAS population by SOC, and PT.

10. Study Treatments and Extent of Exposure

Overall treatment duration will be summarized using descriptive statistics. Individual subject listings will be provided to support the tables.

10.1. Treatment Duration

Summary statistics for treatment duration (in weeks), as well as a frequency summary of treatment duration categories (e.g., < 8 weeks, \geq 8 to < 16 weeks, etc.) will be summarized for FAS and safety population. A subject data listing of study drug exposure will be also provided.

Treatment duration (in weeks) will be calculated as (the date of the last dose of IP - the date of first dose of IP +1)/7 and rounded to one decimal place. The specific definitions of the first and last dose dates are given below:

- First dose date: the date of the first dose of IP at Visit 2/ Week 0.
- Last dose date:
 - The date of last dose of IP captured at Visit 7/Week 48 or Early Termination Visit, whichever occurred first.
 - The date prior to Visit 7/Week 48, if the date of last dose of IP is unknown at Visit 7/Week 48
 - The date prior to Early Termination Visit, if the date of last dose of IP is unknown at Early Termination Visit
 - The last known study date if the subject is lost to follow-up

Imputation rules for partially or completely missing last dose date is specified in Appendix [A1 1](#).

10.2. Treatment Compliance

Treatment compliance (%) will be calculated for each subject based on the number of tablets dispensed and the number of tablets returned at each visit (except Visit 1). Treatment compliance will be summarized.

The treatment compliance (%) for each subject is calculated as below:

$(100 * \text{the total number of tablets taken}) / \text{the intended total number of tablets that should have been taken over the same period}$

Where the total number of tablets taken = the total number of tablets dispensed – the total number of tablets returned. The intended total number of tablets that should have been taken over the same period is $[(\text{last dose date in the period} - \text{first dose date in the period}) + 1] * 2 - 1$ since the patient only took one dose at study day 1.

Please note that treatment compliance will not be calculated for subjects who have only the dispense record at Visit 2/Week 0 and no other drug accountability records.

Additionally, the number and percentage of subjects will be summarized by compliance categories (e.g., < 75%, \geq 75% to \leq 120%, and > 120%). A subject data listing of drug accountability records will be provided.

11. Protocol Deviations/Violations

The protocol deviations or violations will be identified and assessed by clinical research physician (CRP) or designee throughout all study periods. A list of protocol deviations and important protocol deviations for all subjects for final analysis will be defined and finalized prior to the beginning of any data analyses or the final database lock, whichever occurred first. This listing will also identify which subjects are to be excluded from the per-protocol population.

Protocol deviations and important protocol deviations will be summarized for all subjects and FAS population. Summary tables showing the number and percent of subjects with at least one protocol deviation and important protocol deviations and by each category of protocol deviations and important protocol deviations will be provided. Summary of protocol deviations related to COVID-19 control measures will be provided. Listings of subjects with protocol deviations and important protocol deviations will also be provided.

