## 7. DESCRIPTION OF STUDY TREATMENTS

### 7.1. Description of Investigational Product(s)

The chemical name of apremilast (CC-10004) is N-[2-[(1S)-1-(3-ethoxy-4-methoxyphenyl)-2-(methylsulfonyl)ethyl]-2,3-dihydro-1,3-dioxo-1H-isoindol-4-yl] acetamide.

Apremilast will be provided by Amgen Inc. and labelled appropriately as IP for this study.

Apremilast will be provided as 10, 20, or 30 mg tablets in blister cards for dose titration purposes. Apremilast will also be provided as 30 mg tablets in high-density polyethylene (HDPE) bottles (approximately 80 tablets) with child-resistant caps. The apremilast dosing schedule and dose adjustments to be followed for this study are described in Section 7.2. Please refer to the IB for more details on approved indications, known precautions, warnings, and adverse reactions of apremilast.

Additional information may be included on the label as needed or applicable. Label(s) for IP will contain information as required per local health authority.

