### 7.6. Investigational Product Compliance

Study personnel will review the instructions printed on the package with the study subjects prior to dispensing the IP. Investigational product will be dispensed as noted in the Table of Events, Section 5. The subjects will be instructed to return the IP containers, including any unused medication, to the study site at each visit for tablet counts and reconciliation. Subjects will be asked whether they have taken their IP as instructed at each study visit. Any problems with IP compliance will be reviewed with the subject. If the subject misses 4 or more consecutive days of dosing, Amgen must be contacted to decide whether dosing should resume or whether the subject should be terminated from the Treatment Phase of the study, and enter into the Observational Follow-up Phase.

Gross compliance problems (eg, missing 4 or more consecutive days of dosing or taking less than 75% of the doses between study visits) should be discussed with Amgen. Compliance is defined as taking between 75% and 120% of dispensed IP.

Approved

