## 9.8. Other Topics

### 9.8.1. Investigational Product Compliance (Tablets)

Study medication information will be summarized and subject listings will be provided. Compliance will be estimated by the proportion of subjects who take between 75% and 120% of the intended quantity of study medication.

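### SAP 10.2 counts every unreturned tablet as taken, so subjects lost soon after a dispensing visit can look over-dosed and poor adherers can look compliant

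*SAP*

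**What the plan says.** SAP 10.2 divides tablets taken by tablets intended. The numerator is a running subtraction with no cut-off date: "Where the total number of tablets taken = the total number of tablets dispensed – the total number of tablets returned". The denominator is twice the number of days from first to last dose, minus one, "since the patient only took one dose at study day 1". Subjects are then tabulated as below 75%, 75% to 120%, or above 120%.

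SAP 10.1 sets the last dose date. For one group it is "The last known study date if the subject is lost to follow-up". SAP Appendix A1, section 1.4, defines the last known date in the database as the latest of several dates (visit, laboratory, adverse event, medication and others), so it can fall on or after the last visit.

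The only provision for supply that never comes back is: "Please note that treatment compliance will not be calculated for subjects who have only the dispense record at Visit 2/Week 0" and no other accountability record.

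The Protocol's Table of Events has drug dispensed at Weeks 0, 8, 16, 24 and 36. The Protocol also gives the compliance band twice. Section 7.6 says "Compliance is defined as taking between 75% and 120% of dispensed IP". Section 9.8.1 says "Compliance will be estimated by the proportion of subjects who take between 75% and 120% of the intended quantity of study medication".

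**The concern.** Numerator and denominator can cover different periods. When a subject attends a dispensing visit and is not seen again, the whole supply from that visit enters the numerator, while the denominator may add few days or none. The exemption for subjects with only a Week 0 record does not reach anyone lost after Week 8, 16, 24 or 36. A completer who keeps leftover tablets has the same problem in milder form.

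Two errors follow. The category above 120% can contain subjects who took no extra tablets, which reads as a false over-dosing signal. In the other direction, unreturned supply can lift a poor adherer into the 75% to 120% band and hide real under-dosing.

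The two Protocol definitions are a separate inconsistency. A subject cannot take more than 100% of what was dispensed, so the 120% limit in 7.6 cannot be reached, whereas the same limit in 9.8.1 can.

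**Working it through.** The documents give no compliance result to reproduce, so this is tablet arithmetic.

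**Inputs.** Two tablets a day with one on Day 1 (Protocol 7.2; SAP 10.2). Dispensing at Weeks 0, 8, 16, 24 and 36 (Protocol Table of Events). Bottles of about 80 tablets (Protocol 7.1). A 33-day starter card (Protocol Appendix S), taken as 65 or 66 tablets. The number of bottles per visit is **not stated**, so two cases are shown: (A) exactly the needed tablets dispensed; (B) the fewest whole 80-tablet bottles covering each interval, that is 2 for 8 weeks and 3 for 12 weeks.

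**Tablets intended**, 2 × days − 1:
- Week 8: 2 × 56 − 1 = 111
- Week 16: 2 × 112 − 1 = 223
- Week 24: 2 × 168 − 1 = 335
- Week 36: 2 × 252 − 1 = 503
- Week 48: 2 × 336 − 1 = 671

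**Perfect adherer, all earlier surplus returned, lost right after the visit.** Score = (tablets due so far + supply just dispensed) / tablets due so far.

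| Lost after | A: no surplus | B: whole 80-tablet bottles |
|---|---|---|
| Week 8 | (111 + 112)/111 = 201% | (111 + 160)/111 = 244% |
| Week 16 | (223 + 112)/223 = 150% | (223 + 160)/223 = 172% |
| Week 24 | (335 + 168)/335 = 150% | (335 + 240)/335 = 172% |
| Week 36 | (503 + 168)/503 = 133% | (503 + 240)/503 = 148% |

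**Later last known date.** With the date k days after the visit at day D, the denominator becomes 2(D + k) − 1 and the score falls.
- Case A: it first reaches 120% or less at day 38 after Week 8 (223/187 = 119%), day 29 after Week 16 (335/281 = 119%), day 43 after Week 24 (503/421 = 119%) and day 29 after Week 36 (671/561 = 120%, rounded from 119.6%). At the end of the interval it is 100%.
- Case B: the corresponding days are 49 of 56 after Week 16, 73 of 84 after Week 24 and 59 of 84 after Week 36. After Week 8 the score is still 121.5% at day 56.

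**Half-adherer, lost right after the visit, case A.**
- Week 24: (167.5 + 168)/335 = 100%
- Week 36: (251.5 + 168)/503 = 83%

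Both fall in the 75% to 120% band although true adherence is 50%. In case B the Week 36 figure is (251.5 + 240)/503 = 98%.

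**Completer who returns no surplus, case B.** Total dispensed is 66 + 80 + 160 + 160 + 240 + 240 = 946, so 946/671 = 141%. A 65-tablet card gives the same rounded figure. In case A there is no surplus and no error.

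**Protocol 7.6 read literally, perfect adherence over 48 weeks.** Fewest whole bottles throughout:
- 80 tablets per bottle: 671/946 = 71%
- 75 per bottle: 671/891 = 75%
- 85 per bottle: 671/831 = 81%
- exactly the needed number dispensed: 100%

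**The case against.** The strongest reply is that the problem is narrow and the table carries little weight. Much of that stands. Subjects who stop early are due an Early Termination Visit with drug accountability, and all subjects are told to return unused drug, so among dropouts the error is confined to those who leave without returning supply. The documents give an overall dropout allowance of about 20% (Protocol 9.3) but no rate for loss to follow-up or non-return. SAP 10.2 also plans a listing of accountability records, in which unreturned supply could be spotted. Compliance is not an endpoint, and it reaches the per-protocol set only if the deviation criteria, fixed before lock, use it.

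It can also be said that SAP 10.2 already asks for both quantities over the same period. That phrase qualifies only the denominator; the numerator is written as totals with no cut-off, so the mismatch remains.

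A reader might infer that all subjects lost to follow-up will appear above 120%. The documents do not support that: those with only the Week 0 record get no value, late last known dates bring the score to 120% or below, and poor adherers can land in the middle band.

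A reader might also infer that Protocol 7.6 scores full adherence at 71% and so marks adherent subjects for discontinuation. That does not follow either. The 71% rests on bottle counts that are not stated. The trigger in 7.6 for discussion with the sponsor is expressed in doses between visits, not in dispensed tablets. Section 11.1 lists non-compliance as a reason to stop without citing the 7.6 percentage. The 7.6 definition does not enter the SAP table.

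**Conclusion.** The concern holds in limited form. SAP 10.2 is a stated rule that gives wrong values in a prespecified table for subjects lost soon after a dispensing visit from Week 8 on, and for completers who keep surplus. For lost subjects it does not depend on the bottle assumption: 133% to 201% with no surplus, 148% to 244% with whole 80-tablet bottles, both for perfect adherence and a last known date at the visit. The opposite error, a half-adherer placed in the compliant band, also arises without surplus. The completer figure of 141% does depend on the bottle assumption. How many subjects are affected cannot be judged from the documents, and no planned efficacy or safety estimate uses the percentage.

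The conflict between Protocol 7.6 and Protocol 9.8.1 with SAP 10.2 needs no assumption: one band has two denominators. The 71% is illustrative only, within a range of 71% to 81% for 75 to 85 tablets per bottle at the fewest bottles, and 100% with no surplus.

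**What to change.** In SAP 10.2, compute compliance only through the last visit at which all previously dispensed supply has been accounted for. End numerator and denominator at that same visit, and leave out supply dispensed at or after it. Report tablets never returned as a separate count, with the number of subjects concerned. Under this rule the perfect adherer above scores 100% and the half-adherer 50%, whichever visit precedes the loss.

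The cost is a few sentences in the SAP and a small programming change. The drawback is that the final unreconciled interval is not assessed, so under-dosing just before dropout stays unobserved; the table footnote should say so.

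Separately, Protocol 7.6 must be reconciled with Protocol 9.8.1 and SAP 10.2 so that the 75% to 120% band has one denominator throughout.

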12. SAFETY ANALYSIS

Safety will be evaluated via descriptive statistics and point estimates. Safety summaries will be provided based on all the subjects in the safety population. Individual subject listings will be provided to support the summary tables.

For the analyses of AEs and marked abnormalities, the following point estimates are provided, unless otherwise specified:

- Subject incidence: Subject incidence (i.e., percentage [%] used in a frequency summary) is defined as the number of subjects with the specific event divided by the number of subjects included in the analysis, multiplied by 100. Subjects with multiple occurrences of a specific event in a defined exposure interval will be counted only once in the numerator.
- Exposure-adjusted incidence rate (EAIR) per 100 subject-years: The EAIR per 100 subject-years is defined as 100 times the number of subjects with the specific event divided by the total exposure time (in years) among subjects included in the analysis. Subjects with multiple occurrences of the specific event in a defined exposure interval will be counted only once in the numerator. The exposure time for a subject without the specific event is the treatment duration, whereas the exposure time for a subject with the specific event is the treatment duration up to the start date (inclusive) of the first occurrence of the specific event. The total exposure time in years is calculated by dividing the sum of exposure time in days over all subjects included in the analysis by 364. The EAIR per 100 subject-years is interpreted as the expected number of subjects with at least one occurrence of the specific event per 100 subject-years of exposure to the IP.

In summaries of continuous variables with summary statistics by time point, values for baseline, time point, and change from baseline will be summarized at each time point for subjects who have values at both baseline and the specific post-baseline time point. Frequency summaries of shifts from baseline to post-baseline time points will be provided for subjects who have values at both baseline and each individual specific post-baseline time point. In addition to the scheduled visits, shift summaries will also be provided from baseline to the end of period and to the worst value in a specific post-baseline period.

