4.2.5.1. Treatment-Emergent Adverse Event

A treatment-emergent adverse event (TEAE) is defined as any AE that begins or worsens on or after the date of the first dose of investigational product (IP) and no later than 28 days after the

last dose of IP for subjects who have completed the study or have discontinued early by the time of database cut.

If the treatment-emergent status of an AE is unclear due to a missing/incomplete start date, it will always be considered treatment-emergent, unless shown otherwise by data. Date imputation rules for partially missing AE start dates are described in Appendix [A1 1.1](#).

4.2.5.2. Treatment-emergent Adverse Events Leading to Drug Withdrawal, Leading to Drug Interruption, and Leading to Death, and Drug-related Treatment-emergent Adverse Events

A TEAE leading to drug withdrawal is a TEAE for which the investigator indicates that the action taken with respect to IP is withdrawn permanently (action taken on AE eCRF is recorded as “DRUG WITHDRAWN”). A TEAE leading to drug interruption is a TEAE for which the investigator indicates that the action taken with respect to IP is drug interrupted. A TEAE leading to death is a TEAE for which the outcome is fatal. Relationship to IP is based on the investigator's causality judgment; that is, a drug-related AE is an AE indicated by the investigator to have a suspected relationship to IP.

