5.3. Analysis Periods

In this study, the analysis periods are divided into open label treatment period and observational follow-up period below.

- Open label treatment period – Week 0 to Week 48

This period starts on the day after the first IP is dispensed (Visit 2/Week 0), and stops on either: (1) the completion date of treatment period collected in the eCRF; or (2) the early termination date of treatment period collected in the eCRF; or (3) the last known study date if the subject is lost to follow-up.

- Observational follow-up period – 4 weeks

Subjects who complete the study or early terminate from the study, will be followed up for 28 days after the Visit 7/Week 48 or Early Termination visit. The period starts at the end date of treatment period + 1 and stops on either (1) the completion date of follow-up period in eCRF; (2) the last known study date if the subject is lost to follow-up.

For efficacy analysis, only the open-label treatment period will be used.

For safety analysis, the open-label treatment period and observational follow-up period will be included into the data summary.

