12.1.2. All TEAEs

Summarization of all TEAEs by the following categories will be provided as appropriate:

- Any TEAEs (by SOC and PT, and by PT only)
- Any TEAEs by exposure interval (≤ 1 , > 1 to ≤ 4 , > 4 to ≤ 12 , > 12)
- Any TEAEs by age category (< 65 , ≥ 65 years) and gender
- Any TEAEs by prior methotrexate use (Yes/No)
- Any TEAE by concomitant methotrexate use (Yes/No)

For the summary of any TEAEs by exposure interval, the AE data will be handled per the following rules, unless otherwise specified.

- An event with a start date falling into an exposure interval is considered a new event for that interval.
- Each subject is counted once for either subject incidence or EAIR for each applicable specific TEAE in each exposure interval where an event started.
- The denominator of a subject incidence is the number of subjects with treatment duration exceeding the lower bound of the particular exposure interval, while the denominator of an EAIR is the sum of the exposure time during the exposure interval (up to the first event start date for subjects with at least one event starting in the interval) among the same number of subjects as in the denominator of the corresponding subject incidence.

Summarization of the TEAEs with the following specifications will be provided as appropriate:

- Most frequent TEAEs ($\geq 5\%$; by SOC and PT, and by PT only in descending order of subject incidence)
- Most frequent TEAEs by onset interval and event duration (for special interest of PTs: Diarrhoea, Headache, Nasopharyngitis, Nausea, Hypertension, and Upper respiratory tract infection)
- Any drug-related TEAEs (by SOC and PT)
- Any drug-related TEAEs by exposure interval (refer to Section [12.1.2](#))
- Any serious TEAEs (by SOC and PT)
- Any serious TEAEs by exposure interval (refer to Section [12.1.2](#))
- Any serious TEAEs by age category ($<65, \geq 65$ years) and gender
- Any serious drug-related TEAEs (by SOC and PT)
- Any serious drug-related TEAEs by exposure interval (refer to Section [12.1.2](#))
- TEAEs by maximum severity (by SOC and PT)
- Any TEAEs leading to study drug withdrawal (by SOC and PT)
- Any TEAEs leading to study drug withdrawal by age category ($<65, \geq 65$ years) and gender
- Any TEAEs leading to study drug withdrawal by prior use of psoriatic arthritis medications
- Any TEAE leading to study drug withdrawal by concomitant use of psoriatic arthritis medications
- Any TEAEs leading to study drug interruption (by SOC and PT)

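### Adverse-event EAIRs count events up to 28 days after the last dose but divide by time to the last dose only: about 8–10% too high for uncommon events, about 3–7% for frequent ones, relative to full at-risk time

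*SAP*

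**What the plan says.** **Numerator.** SAP 4.2.5.1 sets the onset window for a TEAE in these words: "begins or worsens on or after the date of the first dose of investigational product (IP) and no later than 28 days after the"; the 28 days are counted from the final dose. SAP 5.3 adds: "For safety analysis, the open-label treatment period and observational follow-up period will be included into the data summary". SAP 12 defines the EAIR as "100 times the number of subjects with the specific event divided by the total exposure time (in years) among subjects included in the analysis". Nothing limits it to events that start on treatment.

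**Denominator.** SAP 12 states that "The exposure time for a subject without the specific event is the treatment duration", and that "the exposure time for a subject with the specific event is the treatment duration up to the start date (inclusive) of the first occurrence". SAP 10.1 computes treatment duration as last dose date minus first dose date plus one day, so the 28 days after the last dose are not in it. SAP 12 then interprets the EAIR per 100 subject-years on the investigational product.

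**Exposure-interval tables.** SAP 12.1.2 assigns an event to the interval in which it starts. It then says: "The denominator of a subject incidence is the number of subjects with treatment duration exceeding the lower bound of the particular exposure interval". The interval EAIR uses exposure time in the interval among those same subjects. The cut-points are 1, 4 and 12, with no unit given; weeks are assumed below. These tables are planned for all, drug-related, serious, and serious drug-related TEAEs.

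**The concern.** A rate needs events and time from the same window. Here the window for events is four weeks longer than the window for time. Those four weeks are planned, observed time: SAP 4.1 sends completers and early discontinuers alike into follow-up, and Protocol 6.5.8 and 10.1 record adverse events to 28 days after the last dose.

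Three consequences follow:

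- The EAIR, which Protocol 9.7 introduces to account for exposure, is not the quantity that SAP 12 says it is.
- In the interval tables the numerator is not a subset of the denominator.
- For a first event after the last dose, SAP 12 does not say whether that subject's time stops at the last dose or runs to onset, so two programmers could obtain different numbers.

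The study has a single arm, so these are read as absolute rates and no control arm cancels the error.

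**Working it through.** **Inputs.** Planned treatment is 48 weeks = 336 days (SAP 4.1). The post-dose window is 28 days (SAP 4.2.5.1). Dropout is about 20% (SAP 4.3), with no timing given, so timing is assumed. The plan states no EAIR or person-time total, so there is none to reproduce. The one design figure used does reproduce: (1.96 × 6.2/1.24)² = 96.04, and 96.04/0.80 = 120.05, against the stated 120.

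**1. Uncommon events.** When few subjects have the event, the excess over the same events divided by full at-risk time is 28 / mean treatment days.

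| Dropout (assumed timing) | Mean treatment days | Excess |
|---|---|---|
| None | 336 | 28/336 = 8.3% |
| 20%, uniform | 0.8 × 336 + 0.2 × 168 = 302.4 | 28/302.4 = 9.3% |
| 20%, all at Week 8 | 0.8 × 336 + 0.2 × 56 = 280 | 28/280 = 10.0% |
| 20%, all on Day 1 | 0.8 × 336 + 0.2 × 1 = 269 | 28/269 = 10.4% |

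**2. Frequent events.** A subject who has had the event adds no later time, so the excess shrinks. With a constant hazard and 48-week incidence p, the ratio for completers is [1 − (1 − p)^(364/336)] / p. At p = 0.50 this is (1 − 0.472)/0.50 = 1.056. Adding 20% uniform dropout gives:

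| 48-week incidence | Excess over full at-risk rate |
|---|---|
| 1% | 9.2% |
| 10% | 8.8% |
| 25% | 8.1% |
| 50% | 6.7% |
| 72.7% | 5.1% |
| 90% | 3.3% |

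The 72.7% is the share with at least one AE over Weeks 0–52 in the earlier studies (Protocol Table 10), used as an illustration. At that incidence the SAP rule gives 147.5 per 100 subject-years against 140.4; at 10% it gives 12.4 against 11.4. For a first event after the last dose, running time to onset instead of stopping at the last dose changes the excess little (4.8% instead of 5.1% at 72.7% incidence).

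**3. Against the on-drug rate.** Take events with onset on treatment over treatment time as the reference. At 1% incidence the excess is 9.2% if the hazard is unchanged off drug, 4.6% if it halves, and 0 if no event starts off drug. For a front-loaded event (13.2% by Week 16, as for diarrhea at 30 mg BID in Protocol Table 8, with 12% assumed in the first four weeks) it is 2.4%, against 9.0% on the full at-risk reference.

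**4. Exposure intervals (weeks assumed).**

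- A subject stops at Week 3 and has an event in Week 5. Onset is within 28 days of the last dose, so the subject is in the >4 to ≤12 numerator. Treatment duration is 3, which does not exceed 4, so the subject is not in the denominator. Both the interval percentage and the interval EAIR are wrong.
- A subject who stops at Week 8 has 28 counted days in that interval and 28 uncounted at-risk days: 28/28 = 100%.
- A completer in the >12 interval has 336 − 84 = 252 counted days: 28/252 = 11.1%.

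**The case against.** The strongest reply is that this is a modest clarification to descriptive safety tables. No test or decision rule uses an EAIR, overall subject incidence is reported alongside and is unaffected, and all AEs are listed. That stands and limits the weight of the point, but it does not make the stated rule correct.

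A reader might also infer more than the documents support:

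- **That every rate is 8–10% too high.** That range is near the ceiling and applies to uncommon events. Frequent rows are lower.
- **That the rate is always above the true on-drug rate.** This needs events to start off drug. Protocol 6.5.5 says most diarrhea was reported in the first two weeks of treatment, and the plan gives no off-drug hazard. The excess can be zero.
- **That rates for early dropouts are doubled.** Per subject the ratio is large (28/28 = 100% for a stop at Week 4), but no EAIR by dropout status is planned. It reaches the tables only through pooling and the interval summaries.
- **That all EAIRs need 28 more days.** Protocol Table 13 schedules no blood count or chemistry at the follow-up visit, and a TEAE leading to withdrawal or interruption can hardly start after the last dose. Extra time would dilute those rates.
- **That comparisons with other apremilast studies are distorted.** The documents report no EAIRs or EAIR method from those studies.

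SAP 10.1 also sets the last dose to the last known study date for subjects lost to follow-up, which reduces the mismatch for them.

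**Conclusion.** The mismatch is real and nothing elsewhere in the protocol or SAP repairs it. Against full at-risk time, adverse-event EAIRs are about 8–10% too high for uncommon events and about 3–7% for frequent ones. The first range covers anything from no dropout to 20% dropout, mostly early. The second assumes a constant hazard and 20% uniform dropout; with no dropout the frequent-event figures are smaller (5.6% instead of 6.7% at 50% incidence). Against the on-drug rate the excess lies between zero and roughly the same size, depending on off-drug events that the documents do not quantify.

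The interval-table fault depends on none of these assumptions except the unit of the cut-points: the numerator can contain subjects whom the denominator excludes.

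Only descriptive absolute safety rates are affected. The correction is worth making because the rule as written gives a wrong rate and is cheap to repair.

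**What to change.** In SAP 12 and 12.1.2, use the same window for numerator and denominator. Choose one option and state it:

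- **On-treatment rate.** In EAIRs and interval tables, count only events with onset on or before the last dose, and keep treatment duration as the denominator. Continue to report subject incidence for all TEAEs. This matches the SAP's own interpretation of the EAIR.
- **At-risk rate.** For adverse-event EAIRs and interval tables only, define time at risk as first dose to the earliest of first event, last dose + 28 days, or last contact. Include a subject in an interval if still at risk when it begins.

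Under either option, keep treatment duration as the denominator for marked laboratory abnormalities and for TEAEs leading to drug withdrawal or interruption. State the unit of the interval cut-points, and how time is counted for a first event after the last dose.

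Replacing 364 by 365.25 days per year is not needed: 364/365.25 lowers every rate by only 0.3%.

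The cost is SAP wording and one derived variable; the dates are already collected.
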